9.3.2 Safety and effectiveness outcomes

For each outcome, potential cases will be identified using ICD-9-CM diagnostic codes ([Annex 3](#)) from hospital discharge diagnosis records.

For the purpose of this study, clinically relevant bleedings will be defined as bleedings leading to hospital admission. This restriction is needed to minimize differential misclassification caused by the variability in patients' behavior in seeking care for less severe bleedings. Similarly, the physicians'

attitude towards recording these events may differ between new drugs and standard of care. The consequence of restricting to bleedings identified through hospitalization or referrals is that bleedings leading to death before contact with a health care professional or hospital admission will be ignored. It is assumed that the number of bleeding events missed due to this restriction is small. Nevertheless, the magnitude and impact of this restriction will be assessed in another study of this PASS program (Swedish Record-linkage study).

9.3.2.1 Occurrence of intracranial haemorrhage, gastrointestinal bleeding and urogenital bleeding: case definitions

Intracranial haemorrhage (Annex 3, Table 4)

Cases of intracranial haemorrhage will be identified in patients admitted to the hospital that meet the criteria for one of the three following categories:

- incident cases of intracerebral haemorrhage recorded following or in association with computed tomography, magnetic resonance imaging (MRI) or x-ray angiography, or an appropriate therapeutic procedure.
- incident cases of subarachnoid haemorrhage recorded following computed tomography, MRI, X-ray angiography or lumbar puncture, or an appropriate therapeutic procedure.
- incident cases of epidural, dural, subdural and arachnoid haemorrhage recorded following computed tomography, MRI, x-ray angiography or lumbar puncture, or an appropriate therapeutic procedure.

As therapeutic procedures are not captured in the database, potential cases will be identified by hospital discharge diagnoses (ICD-9-CM). PHARMO will apply for chart review on therapeutic procedures to define the case (see [Section 9.4](#)).

Gastrointestinal bleeding (Annex 3, Table 5)

A patient will have to meet the following criteria to be considered a case of gastrointestinal bleeding:

- the specific site of bleeding originating in the upper or lower gastrointestinal tract or, more specifically, in the oesophagus, stomach, duodenum, jejunum, ileum, colon or rectum.
- for upper gastrointestinal bleeding, the lesion type being erosion, gastritis, duodenitis or peptic (gastric or duodenal) ulcer.
- the lesion type being NOT related to cancer.

Cases will be identified by hospital discharge diagnoses (ICD-9-CM).

Urogenital bleeding (Annex 3, Table 6)

A patient will have to be admitted to the hospital for urogenital bleeding, i.e. the specific site of bleeding originating in the urogenital tract.

Cases will be identified by hospital discharge diagnoses (ICD-9-CM).

9.3.2.2 Secondary safety outcome: case definition

Other bleeding leading to hospitalization (Annex 3, Table 7)

A patient will have to meet the following criteria to be considered a case of “other bleeding”:

- admitted to hospital with a bleeding event occurring before hospitalization (i.e. excluding in-hospital bleeding events).

Cases will be identified by hospital discharge diagnoses (ICD-9-CM).

Non-infective liver disease (Annex 3, Table 8)

A patient will have to meet both of the following criteria to be considered a case of non-infective liver disease:

- The patient having been admitted to hospital with acute liver injury.
- Free of cancer, other liver disease (including infectious hepatitis, chronic liver disease etc.), gallbladder or pancreatic disease and alcoholism.

Potential cases will be identified by hospital discharge diagnoses (ICD-9-CM) and chart review will be applied for (see [Section 9.4](#)) to define the case. If chart review is approved and laboratory values are available in the chart, the following additional criterion will be applied: an increase of more than three times the upper limit of the normal range in alanine aminotransferase (ALT) or aspartate aminotransferase (AST), or a combined increase in ALT, AST or alkaline phosphatase (AP) and total bilirubin, provided one of them is twice the upper limit of the respective normal range.

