Detailed descriptive variables will be captured for the population, including co-medications. Primary safety outcomes are the occurrence of hospitalization for intracranial haemorrhage, gastrointestinal bleeding and urogenital bleeding. Other outcomes of interest include hospitalization for bleeding events not defined in the primary outcome (other bleeding), non-infective liver disease, outcomes related to effectiveness (DVT/PE, ischaemic stroke, myocardial infarction), and all-cause mortality.

Data sources

Data will be obtained from a linked cohort created using the PHARMO Database Network. The PHARMO Database Network is a population-based network of healthcare databases and combines data from different healthcare settings in the Netherlands.

Study size

The size of the population receiving rivaroxaban will be dependent on market uptake. Based on an incidence of haemorrhagic stroke in vitamin K antagonist-treated patients of 5 per 1000 person-years, 12,000 rivaroxaban-treated patient-years and 48,000 vitamin K antagonist-treated patient-years would be required to exclude a 50% increased risk of haemorrhagic stroke in rivaroxaban-treated patients compared with vitamin K antagonist-treated patients, with a power of 80%.

Data analysis

The patient populations will be described according to the descriptive variables, overall and stratified by indication where possible (VTE prevention, DVT/PE treatment, SPAF, ACS, other), naïve or non-naïve status, and switching status. Age- and sex-adjusted odds ratios and 95% confidence intervals (CI) for the descriptive variables, will be computed using logistic regression models both overall and stratified by indication and by naïve or non-naïve status, and switching status.

Crude incidence rates for the safety and effectiveness outcomes will be estimated in the cohorts for DVT/PE treatment, SPAF and ACS. Incidence will be computed using the person–time contribution of the study cohorts, stratified into current, recent, past and non-use.

Age- and sex-adjusted rate ratios with 95% CIs will be estimated for each of the three primary adverse outcomes comparing rivaroxaban with standard of care using Poisson regression analysis based on person–time contribution.

Milestones

Data collection will start from 10 December, 2011 (day after rivaroxaban received marketing authorization for DVT treatment in the Netherlands) and finish on 31 December, 2018.

5 Amendments and updates

Table 1: Amendments

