9.2 Setting

Study drug users will be selected from the outpatient pharmacy database. This database records all outpatient dispensings from primary and secondary care in a well-defined geographic area. All study drug users living in this area will be captured in the database. All patients aged 2 years and above who have been registered in the database for at least 1 year before the index date will be included. A sub-population will be defined of patients for whom GP recorded information is also available.

The enrolment period will start on December 10, 2011 (the day after rivaroxaban received first marketing authorization in the Netherlands for the ‘treatment of DVT and long-term secondary prevention of recurrent DVT and PE’). End of enrolment will be 31 December 2017 and end of follow-up will be 31 December 2018. Interim reports will be provided for data collected 2 and 4 years after the date that rivaroxaban receives reimbursement approval for DVT treatment (see [Section 6](#) for detailed milestones). The characteristics of the two study cohorts in the first year and subsequent years of the enrolment period will be compared.

The drug utilization analysis ([Section 8.1.1](#)) will be performed in the sub-population captured by both the outpatient pharmacy database and the GP database, in order to enrich the data for the assignment of indication of use.

The Adverse Outcomes analysis (Sections [8.1.2](#) and [8.2](#)) will be performed in the full rivaroxaban cohort (outpatient pharmacy database with outcomes available from Medical Register), using the dosing as a proxy for the indication when this information is not available, and in the subcohort of comparator drug users captured by both the outpatient pharmacy database and the GP database.

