9.7.2 Safety and effectiveness outcomes

The two cohorts (of first-time users of rivaroxaban and first-time users of standard of care) will be followed up from the index date until 12 months after the end of the enrolment period for potential outcomes (safety and effectiveness). For each outcome, the first hospitalization for that outcome during the follow-up period will be identified. A separate follow-up will be performed for each of the outcomes.

For all outcomes (for DVT/PE treatment, SPAF and ACS), crude incidence rates will be estimated in both cohorts, using an as-treated approach. In this, person–time will be categorized into current, recent, past and non use. Current use will refer to person–time up to 7 days after the end of supply of the index drug, recent use will refer to person–time up to 90 days after the end of current use, past use will include all person–time contribution after the end of recent use up to 1 year after the end of current use, non-use will include all remaining time person–time contribution after past-use until end of follow-up.

Age- and sex-adjusted rate ratios with 95% CIs will be estimated for each of the three adverse outcomes comparing rivaroxaban with standard of care using Poisson regression analysis. Where numbers and data permit, adjustment will be made for relevant co-medication (described in the drug utilization section), indication and previous hospitalization for bleeding.

As a general strategy, no data imputation strategies will be applied to supplement missing data. The requirement for inclusion is complete data for critical variables such as exposure to rivaroxaban or standard of care and hospitalizations for bleedings or any other outcome event; otherwise this individual is not eligible to be a member of the study population. However, missing values may occur for potential confounder or effect modifying variables. In this case, individuals with missing values will be kept in the analysis and a separate category will be created for missing values of that variable. In sub-analyses to evaluate confounding or effect modification by variables with a large proportion of missing values, the evaluation will be considered to be conducted on the subset with complete data for the variable of interest.

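### Non-infective liver disease: patients barred from being cases stay in the person-time denominator, so the crude rate has no matching population at risk

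*Protocol*

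**What the plan says.** **Numerator.** Protocol section 9.3.2.2 states: "A patient will have to meet both of the following criteria to be considered a case of non-infective liver disease". The first criterion is an admission with acute liver injury. The second is that the patient is "Free of cancer, other liver disease (including infectious hepatitis, chronic liver disease etc.), gallbladder or pancreatic disease and alcoholism". No time point is attached to the second criterion. Potential cases come from the discharge codes in Annex 3 Table 8, and chart review is to be applied for. Section 9.4 makes chart review depend on approval by the database provider and by each hospital.

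**Denominator.** Section 9.2 admits everyone who meets an age and a registration condition: "All patients aged 2 years and above who have been registered in the database for at least 1 year before the index date will be". Neither section 9.1 nor section 9.2 excludes anyone for the conditions listed in the liver definition. Under section 9.7.2 the two cohorts "will be followed up from the index date until 12 months after the end of the enrolment period for potential outcomes (safety and effectiveness"). The same section adds "A separate follow-up will be performed for each of the outcomes", but for each outcome it specifies only that the first hospitalization is taken.

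**Measure.** For all outcomes, "crude incidence rates will be estimated in both cohorts, using an as-treated approach" (section 9.7.2). The Abstract describes the denominator: "Incidence will be computed using the person–time contribution of the study cohorts, stratified into current, recent, past and non-use". Adjustment is confined to the bleeding outcomes: "Age- and sex-adjusted rate ratios with 95% CIs will be estimated for each of the three primary adverse outcomes" (Abstract). Liver disease therefore gets crude rates only.

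**The concern.** A person-time rate is interpretable when everyone in the denominator could, at that moment, enter the numerator. Here the protocol fixes both sides, and they do not match. A patient with, say, a cancer diagnosis before the index date cannot be a liver case but contributes follow-up until the study ends.

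Two things are at stake. The liver rate does not refer to any defined population. And when the two cohorts' crude rates are set side by side, a difference in the share of barred patients would look like a difference between drugs.

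The plan offers little means of noticing this. The baseline characteristics in section 9.3.1 do not include the excluding conditions, and no adjusted liver comparison is planned. Sections 9.2 and 9.4 also use the full rivaroxaban cohort but only those comparator users who have GP data, and section 9.3.2.2 does not say which source establishes that a patient is free of the conditions. If GP records were used wherever they exist, the exclusion would be applied more completely to comparators.

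**Working it through.** **The plan's own figures.** The protocol gives no rate, prevalence or power figure for liver disease. Its only size calculation concerns haemorrhagic stroke: 12,000 × 0.005 = 60 and 48,000 × 0.005 = 240 events; SE = √(1/60 + 1/240) = 0.144; power = Φ(ln 1.5/0.144 − 1.96) = 80.2%, against the stated 80% (two-sided 5% assumed). It reproduces but has no bearing here.

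**Inputs.** The structure comes from sections 9.2, 9.3.2.2 and 9.7.2, the Abstract and Annex 3 Table 8. Every value of p and k below is an assumption.

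**1. Definition enforced.** Let T be total person-time, p the share of T during which patients are barred, and r the rate in patients who can be cases.
- Cases = r(1 − p)T, so the crude rate = cases/T = r(1 − p).
- p = 0.05 gives 0.95r; p = 0.10 gives 0.90r; p = 0.20 gives 0.80r.
- For a condition that arises during follow-up, only the time after onset counts towards p. Earlier time is properly at risk.

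**2. Effect on the comparison.** With equal r in both cohorts, the crude ratio of rivaroxaban to standard of care is (1 − pR)/(1 − pS).

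| pR | pS | Ratio |
|---|---|---|
| equal | equal | 1.00 |
| 0.05 | 0.10 | 0.95/0.90 = 1.056 |
| 0.10 | 0.05 | 0.90/0.95 = 0.947 |
| 0.05 | 0.20 | 0.95/0.80 = 1.19 |
| 0.20 | 0.05 | 0.80/0.95 = 0.842 |

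**3. Definition not enforced.** Table 8 contains diagnoses of chronic liver disease: 571.40, 571.41, 571.49, 571.5, 571.6, 571.8, 571.9 and 572.8. The case definition excludes chronic liver disease. Annex 3 gives no code list for the excluding conditions, and chart review may be refused. If Table 8 codes are simply counted, barred patients enter the numerator. Let k be their rate relative to r. The crude rate is then r[(1 − p) + pk].
- p = 0.10, k = 1: 0.90 + 0.10 = 1.00r
- p = 0.10, k = 2: 0.90 + 0.20 = 1.10r
- p = 0.10, k = 5: 0.90 + 0.50 = 1.40r

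Setting k = 0 returns step 1. How far the exclusion is enforced therefore decides the sign of the error.

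**The case against.** **Ordinary SAP detail.** An outcome-specific population at risk is often left to an analysis plan, and the separate follow-up per outcome is where it would sit. This stands in part, since an SAP may exist. But the protocol does more than stay silent: it states the case rule, the eligible population, the start and end of follow-up, and the person-time used, and these do not fit together.

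**Timing.** The exclusion could be judged at the admission, to rule out other causes of the injury, much as section 9.3.2.1 requires a gastrointestinal lesion unrelated to cancer. This stands for conditions that arise during follow-up: the time before onset is valid. It does not rescue the rest. The liver wording describes the patient rather than the lesion, so someone with a lasting excluding condition before the index date is barred from the first day.

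**Little depends on the comparison.** Section 8.2 asks only for the occurrence of liver disease, without the comparison it requests for other bleeding. Crude rates that are not adjusted even for age and sex cannot carry a drug effect. This stands and limits the consequence.

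**The stronger reading.** A reader might infer that the incidence is understated and differs between the cohorts, for instance because cancer is common in venous thromboembolism. The documents do not support that. They give no prevalence in either cohort. The Abstract estimates rates in the cohorts for DVT/PE treatment, SPAF and ACS, so cancer would matter only if it differed by drug within an indication. Table 8 also leaves the direction open.

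**Conclusion.** The point holds as a mismatch between stated rules. If the definition is applied strictly, the crude liver rate is (1 − p) times the rate in patients who can be cases. The between-cohort ratio may be distorted by (1 − pR)/(1 − pS): about 5–6% for assumed shares of 5% and 10%, about 16–19% for 5% and 20%, and nothing if the shares are equal. If Table 8 codes are counted without the exclusion, the rate may instead be overstated, by 10% to 40% for p = 0.10 and k from 2 to 5.

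Neither an understatement nor a difference between cohorts is established, because the protocol gives no p and does not say how the exclusion will be enforced. The primary bleeding outcomes are untouched. This is a secondary outcome with crude rates only, but the defect is cheap to remove and should be removed before the outcome analysis.

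**What to change.** For this outcome only, in this order:

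1. Reconcile Annex 3 Table 8 with section 9.3.2.2 by separating codes for acute liver injury (the outcome) from codes for excluding conditions. This must come first. Otherwise, censoring at other liver disease would collide with codes that now count as events.
2. Exclude patients with an excluding discharge diagnosis before the index date.
3. End follow-up at the first excluding diagnosis that precedes a liver event, and keep the earlier person-time. State how an excluding diagnosis recorded at the liver admission itself is handled.
4. Apply the same code list, look-back and data source to both cohorts. Hospital discharge records are available for both, whereas GP data are not available for all rivaroxaban users.

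**Cost.** A code list to write, a short addition to section 9.7.2, and slightly less person-time for this outcome. No new data are needed. Discharge records will capture some conditions incompletely: section 9.9 notes that recording of secondary diagnoses is not mandatory and that alcohol intake is poorly recorded. Some barred person-time will therefore remain, and the report should say so.

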9.3.2.3 Secondary outcomes related to effectiveness

DVT and PE (Annex 3, Table 9)

A patient will have to meet the following criteria to be considered a case of DVT or PE:

- the patient having been admitted to hospital with a diagnosis of DVT or PE
- or
- having a DVT or PE diagnosis documented in the general practitioner database.

Ischaemic stroke (Annex 3, Table 10)

A patient will have to meet the following criteria to be considered a case of ischaemic stroke: the patient having been admitted to hospital with a diagnosis of ischaemic stroke.

MI (Annex 3, Table 11)

A patient will have to meet the following criteria to be considered a case of MI: the patient having been admitted to hospital with a diagnosis of MI.

9.3.2.4 Deaths (all-cause mortality)

Date of death is available in the PHARMO database network, as registered in the different databases (GP, pharmacy, hospital deaths) and confirmed through linkage with the Dutch central bureau of genealogy.

9.4 Data sources

Data for the study will be obtained from a linked cohort created using the PHARMO Database Network. The PHARMO Database Network is a population-based network of healthcare databases and combines data from different healthcare settings in the Netherlands. These different data sources are linked on a patient level through validated algorithms. Detailed information on the methodology and the validation of the used record-linkage method can be found elsewhere ([van Herk-Sukel et al. 2010](#); [Herings RMC 2012](#))

The longitudinal nature of the PHARMO Database Network system enables follow-up of more than 4 million residents (25% of total population) of a well-defined population in the Netherlands for an average of ten years. Data collection period, catchment area and overlap between data sources differs. Therefore, the final cohort size for any study will depend on the data sources included. As data sources are linked on an annual basis, the average lag time of the data is 1 year. All electronic patient records in the PHARMO Database Network include information on age, sex, socio-economic status and mortality. Other information available is dependent on the data source

To address the objectives of the present study, the following data sources will be used: outpatient pharmacy database, Dutch National Medical Register, general practitioner (GP) data and inpatient pharmacy database. The outpatient pharmacy database has a source population of about 4 million residents and is fully linked to the national Dutch National Medical Register. The GP and inpatient pharmacy databases each represent different, partially overlapping subsets of the outpatient pharmacy/Medical Register source population.

The drug utilization analysis will be performed in the subpopulation captured by both the outpatient pharmacy database and the GP database, in order to enrich the data for the assignment of indication of use. The Adverse Outcomes analysis will be performed in the full rivaroxaban cohort (outpatient pharmacy database with outcomes available from Medical Register), using the dosing regimen as a proxy for the indication when this information is not available, and in the subcohort of comparator drug users captured by both the outpatient pharmacy database and the GP database.

The PHARMO Network has been used in previous studies of anticoagulant use and bleeding risk ([Penning-van Beest et al. 2005](#); [Penning-van Beest et al. 2007](#); [Penning-van Beest et al. 2008](#); [van der Linden et al. 2009](#)).

Hospital discharge diagnoses in the Dutch National Medical Register are recorded using ICD-9-CM codes. Currently, Dutch hospitals are transitioning from ICD-9 to ICD-10 coding but the majority of hospitals still uses ICD-9. PHARMO will update the code lists to include ICD-10 codes as soon as most admissions are in ICD-10.

PHARMO can apply for chart review to extract additional information about a case in the hospital where he/she was admitted. However, approval is needed from the database provider (Dutch National Medical Register) as well as the individual hospitals.

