9.3 Variables

9.3.1 Patient characteristics and drug utilization

Descriptive variables of drug utilization will be presented only for the subpopulation captured by both the outpatient pharmacy database and the GP database, as only in this subpopulation sufficient information for the assignment of the indication of use is available. The following characteristics, including risk factors/potential confounders for the outcomes under study, will be presented for comparison between the two cohorts:

- age and sex distribution at index date 
- dose of index drug at index date (not available for vitamin K antagonists as dosing is determined in anticoagulation clinics) 

- dispensed amount (can be used to estimate duration of treatment) ✓
- where available based on hospital discharge diagnosis or from available GP notes, diagnosis associated with the prescribing of the index drug (where not available, dose and duration of index drug will be used as a proxy for the associated diagnosis among rivaroxaban users). Hospital discharge diagnoses and procedures will be identified within 4 weeks before until 7 days after the index date and GP diagnosed will be identified during the index month or in the month before the index date.
- proportion of patients defined as naïve, non-naïve, recent switchers and distant switchers ✓
- number of pregnant women at index date (if communicated by midwife or gynaecologist) ✓
- number of pregnancies after index date (if communicated by midwife or gynaecologist) ✓
- type of other anticoagulant use before the index date among the non-naïve group ✓
- use of specific prescribed medications both in the year before the index date and following the index date, confirming the ACS indication: antiplatelet drugs (low-dose acetylsalicylic acid, clopidogrel, dipyridamole, prasugrel, ticlopidine and ticagrelor); ✓

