9.5 Study Size

All patients registered in the PHARMO outpatient pharmacy database and meeting the inclusion criteria will be included. The size of the population receiving rivaroxaban will be dependent on market uptake across the indications of interest (DVT/PE treatment, ACS and SPAF).

According to a preliminary sample size calculation, based on an incidence of haemorrhagic stroke in vitamin K antagonist-treated patients of 5 per 1000 person-years, 12,000 rivaroxaban-treated patient-years and 48,000 vitamin K antagonist-treated patient-years would be required to exclude a 50% increased risk of haemorrhagic stroke in rivaroxaban-treated patients compared with vitamin K antagonist-treated patients with a power of 80%.

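### Socio-economic status is recorded for every patient but is in neither the listed baseline characteristics nor the named adjustment set, although the two arms of the outcome analysis are drawn from different source populations

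*Protocol*

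**What the plan says.** Section 9.4 of the protocol describes the content of the network: "All electronic patient records in the PHARMO Database Network include information on age, sex, socio-economic status and mortality".

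Section 9.3.1 introduces its list of variables with "The following characteristics, including risk factors/potential confounders for the outcomes under study, will be presented for comparison between the two cohorts". The list is long. It includes age, sex, dose, indication, co-medication, renal status, smoking, body mass index, earlier admissions for bleeding and healthcare utilization. Socio-economic status is not on it.

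Section 9.7.2 fixes the outcome model in two steps. The core is "Age- and sex-adjusted rate ratios with 95% CIs will be estimated for each of the three adverse outcomes comparing rivaroxaban with standard of care", by Poisson regression. Then: "Where numbers and data permit, adjustment will be made for relevant co-medication (described in the drug utilization section), indication and previous hospitalization for bleeding". Socio-economic status is in neither step. The objectives (8.2), sub-cohorts (9.7.2.1), sensitivity analyses (9.7.2.2) and limitations (9.9) do not mention it either.

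Sections 9.2 and 9.4 define who is compared. The rivaroxaban arm is the full cohort from the outpatient pharmacy database. The comparator arm is the subset of users who are also in the GP database. Section 9.7.2.1 adds that the component databases cover different geographical areas.

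**The concern.** Of the four items that 9.4 says are in every record, socio-economic status is the only one that the plan never uses. This would matter little if both arms came from the same population. They do not: one arm is restricted to the GP catchment and the other is not. A difference in area between the arms can bring a difference in socio-economic status with it, whatever drives the choice of drug.

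The plan has one general safeguard. Section 9.7.2.2 expects the drug utilization data to reveal unexpected biases, which the outcome analysis can then take into account. That check misses this imbalance for two reasons. The data it relies on, as listed, do not include socio-economic status. And the drug utilization part is confined to patients in both the pharmacy and GP databases, so it does not compare the two groups that enter the rate ratios.

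At stake are the three primary bleeding rate ratios, if status is also related to bleeding, and the description of the two user groups, which is itself a primary objective (8.1.1).

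**Working it through.** **The plan's own figure.** Section 9.5 gives 5 events per 1,000 person-years, 12,000 rivaroxaban and 48,000 vitamin K antagonist patient-years, a ratio of 1.5 to be excluded, and 80% power, for haemorrhagic stroke. No alpha is stated; I assume two-sided 0.05.

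- Expected events with a true ratio of 1: 0.005 × 12,000 = 60 and 0.005 × 48,000 = 240.
- SE of the log rate ratio: √(1/60 + 1/240) = 0.144.
- Power: Φ(ln 1.5 / 0.144 − 1.96) = Φ(0.849) = 80.2%.

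The stated size reproduces, and adding a covariate does not change it. It serves here as a yardstick.

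**Size of a possible bias.** The documents give no distribution of socio-economic status and no relation of it to drug choice or bleeding, so every input is an assumption. For a binary low-status group with share p1 in rivaroxaban users and p0 in comparator users, and bleeding rate multiplied by r in that group, the unadjusted ratio is multiplied by

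B = [1 + p1(r − 1)] / [1 + p0(r − 1)].

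Take p0 = 0.30, with p1 between 0.25 and 0.10:

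| r | p1 = 0.25 | p1 = 0.10 |
|---|---|---|
| 1.2 | 1.05/1.06 = 0.991 | 1.02/1.06 = 0.962 |
| 1.5 | 1.125/1.15 = 0.978 | 1.05/1.15 = 0.913 |
| 2.0 | 1.25/1.30 = 0.962 | 1.10/1.30 = 0.846 |

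If the shares are swapped between the arms, the factor is the reciprocal: from 1/0.991 = 1.01 to 1/0.846 = 1.18. If p1 = p0 or r = 1, it is exactly 1.00.

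**Against the precision of the study.** ln 0.991 = −0.009, or 0.07 SE; ln 0.846 = −0.167, or 1.16 SE. The middle value at r = 1.5, p1 = 0.10 is ln 0.913 = −0.091, or 0.63 SE.

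**Against the purpose of excluding 1.5.**

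- Downward bias, true ratio 1.5: expected events are 90 and 240, SE = √(1/90 + 1/240) = 0.124. The chance of wrongly excluding 1.5 is 1 − Φ(1.96 + ln B / 0.124). This is 2.5% at B = 1, 3% at 0.991, 11% at 0.913 and 27% at 0.846.
- Upward bias, true ratio 1, holding the SE at 0.144: power is Φ[(ln 1.5 − ln B)/0.144 − 1.96]. This falls from 80% to 78% at B = 1.01 and to 38% at B = 1.18.

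The outer values need both a doubling of the bleeding rate and a 20-point imbalance. They bound the illustration and are not a forecast.

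**The case against.** The strongest case against is that this is a preference about covariates. The protocol contradicts nothing, misstates no figure and does not say that its adjustment set is closed; a fuller list could sit in a statistical analysis plan. Section 9.4 describes the network in general and does not say whether socio-economic status is individual or area-level, how it is categorised or how complete it is. The formula also ignores whatever part of the effect age, sex and co-medication already absorb. All of this stands, and it keeps the point small. It does not remove it: the protocol itself itemises the potential confounders and names the adjustment terms, and both leave out a variable that it says is in every record.

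Three stronger readings are tempting, and the documents support none of them.

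- A reader might infer that access to rivaroxaban depended on means before it was reimbursed. Reimbursement appears in 9.2 only to time reports: "Interim reports will be provided for data collected 2 and 4 years after the date that rivaroxaban receives reimbursement approval for DVT treatment". Section 9.5 links numbers to market uptake across indications and says nothing of payment.
- A reader might infer that the rate ratios are confounded in favour of rivaroxaban. No relation of socio-economic status to drug choice or to bleeding is given, so neither the existence nor the direction of a bias is shown.
- A reader might treat socio-economic status as a stand-in for the alcohol intake and over-the-counter drug use that 9.9 lists as possible unmeasured confounders. The protocol does not say that it captures either.

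**Conclusion.** The omission is real, and the documents give a reason to care about it: the arms come from populations with different catchments, and the planned bias check cannot see this variable. Socio-economic status is a potential confounder of unknown size and direction. On assumed inputs (30% low status in one arm and 10% to 25% in the other, bleeding rate 1.2 to 2 times higher in that group) the rate ratio would be off by about 1% to 15% downward, or 1% to 18% upward with the shares swapped. It would be off by nothing if status is balanced between the arms or unrelated to bleeding. The point is minor, and worth acting on because the remedy is cheap.

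**What to change.** Add socio-economic status, in the database's own categories, to the 9.3.1 characteristics. Because that comparison is limited to the GP subpopulation, also tabulate it for the two groups that actually enter the outcome analysis. In 9.7.2, make it a standing term in the Poisson model with age and sex, with a separate category for missing values as that section already provides. If the categories prove too coarse or too incomplete to use, say so and give that as the reason for leaving it out.

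The cost is a few degrees of freedom, affordable at about 300 expected events (60 + 240), and the risk that coarse categories remove only part of any confounding. According to 9.4 no new data source is needed.
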